6 TRIAL OUTCOMES

Our primary outcomes are % changes in free sugar intakes and adherence to the dietary recommendations over a 12 week period. Secondary outcomes are: daily energy intake, dietary composition, anthropometry, sweet food perceptions and preferences, sweet food choice, attitudes to sweet foods, attitudes towards eating behaviour, motives for food choice, knowledge and lifestyle variables, quality of life and adverse events. Secondary qualitative outcomes are: barriers and facilitators towards intervention adherence and success/failure in achieving the recommendations. Sweet liker status, PROP status, and demographic variables will also be assessed to aid in the interpretation of all outcomes.

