Three distinct analyses were pre-specified in advance: 1) Analyses of the population as a whole to investigate the effects of the three different types of dietary recommendation versus control; 2) Analyses of the effects of the dietary recommendations in different population subgroups, and 3) Investigation of the barriers and facilitators to success.

Data presentation

Data will be presented as mean \pm standard deviation in all cases, unless stated. Values will be considered significant at the $p<0.05$ level. Before completing analyses, data will be checked for normality. The data set is large, $N=242$, thus a normal distribution will be assumed. Where assumptions of homogeneity of variance are violated (Levene's test $p<0.05$), statistics will be taken from analyses conducted assuming non-equal variances. Bonferroni corrections for multiple testing will be applied to data where tests were not pre-specified in the study protocol. Where multiple regression analyses are used, all variables will be checked for multicollinearity using correlation cut-offs of <0.7 . Pearson correlation values will be used for all continuous variables, and Spearman correlations for categorical variables.

Participant characteristics

Details of study completion will be provided and a CONSORT diagram created detailing number randomized to each group, number completing the study in each group, drop out and number included in all analyses.

Characteristics will be given for the whole sample and for each trial group.

Analyses One: Quantitative Data

For analyses one, multiple regression analyses will be used. Analyses will be conducted for both primary outcomes, for key secondary outcomes - daily energy intake, sugar-sweetened food intake, LCS-sweetened food intake, body weight, waist circumference, and adverse events; and change (baseline - week 12) data for these outcomes; and for other secondary outcomes (dietary

composition, sweet food perceptions and preferences, sweet food choice, attitudes to sweet foods, attitudes towards eating behaviour, motives for food choice, knowledge and lifestyle variables, quality of life) if differences are found in the sample as a whole from baseline to week 12. This will reduce the number of exploratory tests undertaken. Differences from baseline to week 12 will be investigated by paired t-tests. Primary outcomes and outcomes associated with dietary composition will also be investigated in the same manner at weeks 1, 2, 4 and 8.

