Primary models will include gender, age, control/intervention group, baseline %FS, baseline body weight (as randomization variables), and baseline variable of interest. In analyses for %FS, sugar-sweetened food intake, LCS-sweetened food intake, body weight and waist circumference, TEI at Week 12 and physical activity at Week 12 will also be included. Secondary models will also include any additional variable that correlates with each outcome when assessed independently. All variables measured will be considered as secondary variables. Effects for all continuous variables will be investigated using linear multiple regression. Effects for adherence will be investigated using logistic regression to predict adherent vs not adherent.

Analyses Two: Quantitative Data

For analyses two, analyses one will be repeated for demographic groups where significant associations for these variables were found in analyses one. Analyses will only be conducted if significant associations are reported. If no significant associations with demographic variables are found, these analyses will not be completed. These analyses are intended to demonstrate differing effects of the intervention/s in different population groups.

Analyses Three: Qualitative Data

Analyses three will investigate the qualitative data collected from a subset of participants using solo interviews. These interviews were scheduled for completion in a sample of 80 participants from different intervention groups and at different time points. These analyses will be undertaken using a thematic framework analysis. First, a random sample of interviews will be analysed inductively using thematic analysis to identify codes. These codes will be used to create a framework and the framework then applied to all interviews.

Framework analysis has been chosen as a suitable analytical method for evaluating the qualitative interview data gathered, due to an interest in individual experiences and seeks to identify the different factors (barriers or facilitators) that contributed to successful or unsuccessful dietary change (Braun & Clark, 2013). The practical methods for conducting framework analysis follow a methodology as outlined below.

Framework analysis (Braun & Clarke, 2006; 2013; Gale et al, 2013).

Phase 1 'Familiarizing yourself: Transcribing data (if necessary), reading and re-reading the data, noting down with your data: initial ideas'.

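### Spearman correlation is assigned to all categorical variables, so for an unordered category with three or more levels, entry to the secondary models can depend on how its levels were numbered

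*SAP*

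**What the plan says.** Four places matter.

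- **SAP, Data presentation.** The collinearity rule comes first: "Where multiple regression analyses are used, all variables will be checked for multicollinearity using correlation cut-offs of <0.7". The next sentence gives the coefficients: "Pearson correlation values will be used for all continuous variables, and Spearman correlations for categorical variables". Nothing separates two-level, ordered and unordered categories.
- **SAP, Analyses One.** The primary models have a fixed covariate list that includes gender and age. For the rest: "Secondary models will also include any additional variable that correlates with each outcome when assessed independently". The candidate pool is wide: "All variables measured will be considered as secondary variables". No F test, Kruskal-Wallis test, chi-square test or joint test of dummy variables is named for this screen, and no threshold of its own is given.
- **SAP, Analyses Two.** Subgroup analyses depend on what Analyses One finds: "If no significant associations with demographic variables are found, these analyses will not be completed".
- **Protocol, section 6.** The categorical candidates that can be identified are these: "Sweet liker status, PROP status, and demographic variables will also be assessed to aid in the interpretation of all outcomes". Their levels and codes are not given in the documents supplied.

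**The concern.** Spearman's rho is computed on ranks. For a two-level variable, swapping the codes changes only the sign. For an ordered variable, the ranks carry meaning. For three or more unordered levels, the ranks reflect only which level was numbered 1, 2 or 3, so rho and its p-value change when the same data are renumbered.

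If the screen uses this coefficient, a real predictor can be left out of a secondary model, or a chance one let in, because of data-entry order. There is a second step. A demographic variable other than gender and age reaches a regression model only through the screen. If it is screened out, it cannot show the association in those models that would trigger its subgroup analysis.

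**Working it through.** The plan gives no figure to reproduce here, so the check asks how far the selection decision moves when only the numbering changes.

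**Inputs from the SAP:** N = 242; significance at 0.05, taken as two-sided and as the screening threshold, since no other is stated.

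**Assumptions (no source in the documents):** a three-level unordered variable; one level higher by 0.3 to 0.8 SD and the other two equal; group shares of equal thirds, 50/30/20 or 60/25/15. In the unequal splits the second-listed group (30% or 25%) is the shifted one.

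**Step 1: why numbering matters.** Let the groups coded 1, 2, 3 have shares p1, p2, p3, and let the shifted group have share p. On a 0–1 scale the mean rank is 1/2.
- Shifted group in the middle: its mid-rank is p1 + p2/2, so its distance from the mean is (p1 − p3)/2.
- Shifted group at an end: the distance is (1 − p)/2.

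The variance of the tied ranks, (1 − Σp³)/12, does not depend on the order. The expected covariance under a middle code, relative to an end code, is therefore (p1 − p3)/(1 − p):
- equal thirds: 0/(2/3) = 0
- 50/30/20: 0.30/0.70 = 0.43
- 60/25/15: 0.45/0.75 = 0.60

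The signal disappears only when the two outer groups are equal in size; otherwise it is weakened.

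**Step 2: the threshold.** From t = rho × √[(N − 2)/(1 − rho²)] with critical t = 1.97, significance needs |rho| of at least 1.97/√(240 + 1.97²) = 0.126. In equal thirds with a 0.6 SD shift, mean rho is 0.00 under a middle code and about 0.23 in size under an end code.

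**Step 3: simulated selection rates, 0.6 SD shift, N = 242.** For equal thirds the share of variance explained is (2/9 × 0.36)/(1 + 2/9 × 0.36) = 0.074.

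| Group shares | Spearman, middle code | Spearman, end code | One-way F test |
|---|---|---|---|
| Equal thirds | about 5% | 96% | 98% |
| 50/30/20 | 34% | 94% | 96–98% |
| 60/25/15 | 51% | 91–92% | 96–98% |

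**Step 4: other effect sizes** (4000 data sets each; the 0.3, 0.5 and 0.8 SD equal-thirds rows use 3 × 81 = 243).

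| Shift, shares | Middle code | End code | F test |
|---|---|---|---|
| 0.3 SD, equal | 5% | 45% | 48% |
| 0.4 SD, equal | 5% | 68–69% | 73% |
| 0.5 SD, equal | 5% | 86–87% | 91% |
| 0.5 SD, 50/30/20 | 24% | 85% | 90% |
| 0.8 SD, equal | 4% | 99.8–99.9% | 100% |

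At 0.5 SD in equal thirds, the three codings of the same data gave different decisions in 93% of runs. With no true association each coding kept about 5% false selection, but the codings disagreed in 12% of runs.

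**Step 5: where Spearman is sound.** Reversing a two-level variable left the p-value unchanged. For an ordered variable with means 0, 0.25 and 0.5 SD, Spearman in the natural order detected the trend in 87% of runs, against 81% for the F test.

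**Step 6: the collinearity check.** In a constructed example (middle group 6 SD above the others on a covariate), the same data gave rho = −0.01 under codes 1, 2, 3 and 0.70 under codes 1, 3, 2. The cut-off is 0.7.

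**The case against.** **The Spearman sentence may concern only collinearity.** It directly follows that check, and the Analyses One screen names no coefficient. This stands as a caution: the link to the screen is an inference. The other reading does not remove the problem, because the collinearity check then has the same flaw (Step 6) and the screen has no stated method for categorical variables.

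**No affected variable is shown.** This also stands. Gender is coded 1/2, PROP status may well be an ordered scale, and the levels of sweet liker status and the other demographics are not given. The four adherence classes in Protocol section 6.2 have no single natural order, but adherence is a primary outcome that the SAP analyses as two classes, so it is a weak example of a candidate covariate.

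**The 5% figure is a worst case.** Correct. It needs outer groups of equal size and equal mean. A reader might infer that the rule fails for every unordered category. It does not: with an end code, Spearman selects nearly as often as the F test.

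**The treatment comparison is barely touched.** Correct. A reader might infer bias in the primary result, but the primary models have a fixed covariate list and are not screened. In a randomised comparison, a covariate missed from a secondary model mainly costs precision.

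**Analyses Two is not generally blocked.** Correct. Gender and age are in every primary model, so their associations are tested whatever the screen does. Only other unordered demographics with three or more levels could be held back.

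**Conclusion.** The point holds in a limited form and is minor. As written, the rule covers unordered categories, and for those with three or more levels the decision can turn on numbering. At a 0.6 SD shift, selection under a middle code is about 5% to 51% depending on group shares, against 91–96% under an end code and 96–98% by a test that ignores coding.

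This rests on three assumptions: that the Spearman sentence governs the screen, that the general 0.05 level is the screening threshold, and that at least one demographic or taste-status candidate has three or more unordered levels. The effect sizes and group shares are illustrative.

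The harm is confined to the composition of the secondary models, the collinearity check for such variables, and whether unordered demographics other than gender can trigger Analyses Two. The documents do not support a claim that the primary result is biased or that a named variable has been wrongly excluded.

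**What to change.** In the SAP, Data presentation:

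- Limit Spearman to two-level or ordered categories, where it works well.
- For an unordered category with three or more levels, judge association with the outcome by the joint test of its dummy variables: the F test in linear models, and the likelihood-ratio or Wald test in the logistic model for adherence.
- State that such a variable enters the secondary model as dummies.
- For those variables only, check collinearity with a measure that does not depend on coding, for example a generalised variance inflation factor. Pairwise correlations can stay for the other variables; replacing them throughout would be a preference.
- State whether the correlation rule applies to the Analyses One screen as well as to the collinearity check.

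The cost is a sentence or two in the SAP, a few lines of SPSS syntax, and one degree of freedom for each additional category.

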6.4 OUTCOME ASSESSMENT SCHEDULE

An overview of the outcome assessment schedule is given in **Table 2**.

Free sugar intakes and adherence will be assessed throughout the intervention period as given in **Table 1**. All other outcomes will be assessed at baseline and at trial end, with the exception of the following: sweet liker status, PROP taste sensitivity and demographic characteristics will be measured only at baseline; questions on adherence and difficulties will be asked at weeks 4, 8 and 12.

All participants will undertake all measures, in the same manner, regardless of intervention arm. Dietary assessments, questions on adherence and difficulties will be undertaken via the Nutritics software. Self-report questionnaires will be administered online via Qualtrics. Measures associated with taste status and appetite will be presented to participants using a paper format to be completed during a test session.

Compliance with trial measures will be enhanced using a bogus pipeline method (Hugh, 2013; Muhlheim et al., 1997; Reid et al., 2014); participants will be asked to provide a saliva sample at baseline and at trial end, for the supposed purpose of examining salivary enzymes that may vary with dietary change. In reality, samples will be discarded. Only at the end of the trial will participants be informed that their samples have not been analysed.

Table 2: Schedule of enrolment, interventions and assessments

	Trial period						
	Enrolment	Baseline	Intervention			End	
Time point	Wk -1 / 2	0	Wk 1	Wk 2	Wk 4	Wk 8	Wk 12
Enrolment							
Eligibility screen	X						
Informed consent	X						
Allocation		X					
Intervention							
Intervention groups							→
Control group							→
Assessments							
24hr diet diary							→
3 day diaries	X	X					X
Adherence							→
Adherence questions					X	X	X
Anthropometrics		X					X

Sweet liker status		X					
PROP taste test		X					
Sweet taste test		X					X
Sweet food choice		X					X
Sweet attitudes		X					X
TFEQ		X					X
FCQ		X					X
Demographics		X					
Knowledge		X					X
GSLTPAQ		X					X
SF36		X					X
Adverse events							→
Difficulties / Adverse events					X	X	X
Interview			X*	X*	X*	X*	X*
BP cheek swab	X						X

X* Interviews completed only once. TFEQ: Three-factor eating questionnaire; FCQ: Food choice questionnaire; GSLTPAQ: Godin- Shepard leisure time physical activity questionnaire; SF-36: Short-form 36 measure of quality of life; BP: Bogus pipeline method.

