7.4 WITHDRAWAL AND DEBRIEFING

Participants will be considered as having withdrawn from the trial if they either express this or they do not attend the final test day. If individuals fail to report diet diaries, they will be sent reminders however, data will be noted simply as 'missing' while the participant continues in the trial.

Individuals will be debriefed on exit, or at their original 12-week intervention end time-point if other household members are partaking. During the debrief session, participants will be asked for their understanding of the trial purpose to investigate the success of the methods to disguise the trial aims, and will then be debriefed on the true purpose of the trial. Following the debrief session, participants will be offered a consultation on their diet, by a Registered Associate Nutritionist, as a thank you for taking part.

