BLNFS, BLDGendermale1female2, BLBMI, BLNEnergykcal, BLNCarbohydrateg, BLNProteing, BLNFatg, BLN Sugarsg, BLNFreeSugarsg, BLNFibreg, BLNSaturatedFatg, BLSSodiumNamg, BLWeightkg, BLWaistcircumferencecm, BLLTEShealthscore, BLFCQ1Health, BLFCQ2Mood, BLFCQ3Convenience, BLFCQ4SensoryAppeal, BLFCQ5NaturalContent, BLFC1Q6Price, BLFCQ7WeightControl, BLFCQ8Familiarity, BLFCQ19EthicalConcern, BLSQPC1Personalimpact, BLSQPC2Personalmanagement, BLSQPC3Nonchalance, BLSQPC4Negativity, BLSQPC5Perceivedunderstanding, BLSQPC6PerceivedNonautonomy, BLSF36PCS, BLSF36MCS, BLTSEQ CR, BLTSEQQUE, BLTSEQEE. *Followed by imputation only variables

Get pooled descriptives for analysis / comparison to my values.

1. Data - Split file
 - a. Click split file in ComA1_imp
 - b. Click compare groups
 - c. By imputation number_variable
 - d. Ok
2. Analyze – Descriptive statistics
 - a. Descriptives
 - b. Input all BL and EP variables apart from BL OG FS%.
 - c. Scroll to bottom of output table for pooled means – SD will be calculated from average of 20 imputations at a later date and are not shown here.

BLINDING

The main researcher had no knowledge of allocated groups of participants and was blinded during all data handling and imputation.

DATA ANALYSIS

Outcomes

Primary outcomes were % TEI from free sugars (%FS), and adherence to the recommendations at 12 weeks. Secondary outcomes were dietary profiles (daily energy intake, dietary composition, food consumption), anthropometry, sweet food perceptions and preferences, sweet food choice, attitudes to sweet foods, attitudes towards eating behaviour, motives for food choice, knowledge and lifestyle variables, quality of life and adverse events at week 12; change between baseline and week 12 in key outcomes (%FS, daily energy intake, sugar-sweetened and sweetener-sweetened food consumption, anthropometry), %FS, adherence, dietary profiles and barriers and facilitators towards intervention adherence and success/failure in achieving the recommendations (subset only) at weeks 1, 2, 4 and 8. Demographic variables, and sweet taste sensitivity, sweet liker status and PROP (bitter taste) status were also assessed at baseline, to aid in the interpretation of all outcomes, considering associations between these variables and sweet taste perceptions, liking and food intakes (Jayasinghe et al., 2017; Yeomans et al., 2009).

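### The SAP gives adverse events a baseline term and a change score, and no rule for counting events recorded before week 12 or in people who leave

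*SAP*

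**What the plan says.** **SAP, Outcomes.** The secondary outcomes include "quality of life and adverse events at week 12". The same sentence then restricts the change outcomes to "change between baseline and week 12 in key outcomes (%FS, daily energy intake, sugar-sweetened and sweetener-sweetened food consumption, anthropometry". Adverse events are not on that list, nor among the outcomes named for weeks 1, 2, 4 and 8.

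**SAP, Analyses One: Quantitative Data.** Adverse events are a key secondary outcome for multiple regression. The list ends with "body weight, waist circumference, and adverse events; and change (baseline - week 12) data for these outcomes", so here they do get a change score. The primary models include the baseline value of whichever outcome is being modelled. Linear regression is named for continuous outcomes and logistic regression for adherence; no model type is named for adverse events. Interim analyses are limited: "Primary outcomes and outcomes associated with dietary composition will also be investigated in the same manner at weeks 1, 2, 4 and 8".

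**Protocol, section 6.4.** The text says "All other outcomes will be assessed at baseline and at trial end, with the exception of the following". Among the exceptions, "questions on adherence and difficulties will be asked at weeks 4, 8 and 12", but adverse events are not named. Table 2 has one adverse-event row drawn as an arrow through the trial and a second row, "Difficulties / Adverse events", marked at weeks 4, 8 and 12. Neither row shows a baseline mark in the text available.

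**Protocol, section 7.4.** "Participants will be considered as having withdrawn from the trial if they either express this or they do not attend the final test day".

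**The concern.** Body weight exists before allocation and again at week 12, so adjusting for baseline or subtracting it makes sense. An adverse event under study is something that happens after allocation. Its count starts at zero for everyone, so there is nothing to adjust for or subtract. If a baseline symptom report were used instead, the change would mix complaints present before allocation with events arising afterwards.

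The SAP also does not say which records feed the week-12 figure. The trial plans to collect adverse events throughout, but no rule carries the earlier records, or the records of someone who later leaves, into the comparison between arms.

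Adverse events are the only listed outcome that directly records harm. If the window, the model and the handling of leavers are left open, they will be chosen after the data are in hand. An arm difference arising early, or one that leads people to leave, could then go unseen.

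**Working it through.** The plan states no adverse-event rate, power or sample size, so there is no figure to reproduce. The check is a comparison of the texts, followed by an illustration on assumed rates.

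**1. The texts side by side**

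| Question | SAP, Outcomes | SAP, Analyses One | Protocol 6.4 text | Protocol Table 2 |
|---|---|---|---|---|
| Baseline value? | Not mentioned | Required by the model and the change score | Implied, as adverse events are not among the exceptions | No mark visible |
| Change score? | Not listed | Listed | – | – |
| Weeks 1–8? | Not listed | Not analysed | Not named | Ongoing arrow; weeks 4 and 8 marked |
| Week 12? | Yes, window undefined | Yes, window undefined | Trial end | Marked |

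Two contradictions follow. The two SAP sections disagree on the change score, and the 6.4 text disagrees with Table 2 on timing. On either reading of the SAP, the baseline term needs a quantity that Table 2 does not visibly supply.

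**2. What the undefined window could mean**

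Inputs from the documents: 60 per arm and a 20% attrition allowance (protocol 4.2), so 60 × 0.8 = 48 completers. Assumptions: a constant weekly event rate, leavers exiting evenly over 12 weeks (6 weeks on average), and no use of leavers' records.

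Average observed time per randomised person is 0.8 × 12 + 0.2 × 6 = 10.8 weeks. The share of that time covered is:

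- week 12 only, completers: 0.8 × 1 / 10.8 = 7.4%
- weeks 9–12, completers: 0.8 × 4 / 10.8 = 29.6%
- cumulative to week 12, completers: 0.8 × 12 / 10.8 = 88.9%; the remainder is leavers' time.

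**3. Expected people with an event, per arm**

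Let c be the 12-week risk (assumed). The risk over w weeks is 1 − (1 − c)^(w/12). For c = 20%, four weeks give 1 − 0.8^(1/3) = 0.0717 and one week gives 1 − 0.8^(1/12) = 0.0184.

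| Assumed c | All 60, cumulative | 48 completers, cumulative | 48, weeks 9–12 | 48, week 12 only |
|---|---|---|---|---|
| 10% | 6.0 | 4.8 | 1.7 | 0.4 |
| 20% | 12.0 | 9.6 | 3.4 | 0.9 |
| 40% | 24.0 | 19.2 | 7.5 | 2.0 |

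The first count column assumes 12 weeks of follow-up for everyone, so it slightly overstates what would be recorded.

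**4. Power, on assumed risks**

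Two-sided 5% comparison of two proportions: z = (|p2 − p1|√n − 1.96√(2p̄(1 − p̄))) / √(p1(1 − p1) + p2(1 − p2)), and power = Φ(z). For 20% against 40% over 12 weeks:

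- cumulative, n = 60: z = (1.549 − 1.270) / 0.632 = 0.44, power 67%
- weeks 9–12 (7.2% v 15.7%), n = 48: z = −0.66, power 26%
- week 12 only (1.8% v 4.2%), n = 48: z = −1.29, power 10%.

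For 10% against 20% the three figures are 33%, 13% and 6%; for 30% against 50% they are 61%, 24% and 10%.

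**The case against.** A reader might infer that the SAP discards every event from weeks 1 to 11 and removes leavers from the safety comparison. The documents do not support that as fact.

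- **The window is undefined, not shown to be narrow.** An adverse-event outcome at week 12 could mean cumulative to week 12, which would fit Table 2's arrow. Completers would then lose nothing. Section 6.3 sends the assessment details to Supplementary Materials that are not among the documents reviewed. Against this, the phrase closes a list of outcomes that includes anthropometry and quality of life, and Analyses One gives adverse events a baseline and a change. That fits a point-in-time value better, but does not settle it.
- **Leavers are not excluded.** The SAP's main analyses are intention to treat with multiple imputation, and it rejects complete-case analysis. Section 7.4 also does not show that someone who misses the final session has no week-12 entry, since the difficulties questions are answered in the diary software. The risk is narrower: a leaver's recorded events may go unused or be displaced by an imputed value. Whether adverse events are imputed is not shown. The listed baseline sequence contains no adverse-event variable, and the imputation-only variables are not listed.
- **The change score may be loose drafting.** It rests on Analyses One alone. This makes it a contradiction to resolve rather than a settled plan.
- **The missing baseline is partly a matter of legibility.** Where the Table 2 arrow starts cannot be seen, and the 6.4 text taken literally implies a baseline assessment.
- **The figures are illustrative.** The 48-per-arm rows treat leavers as contributing nothing, which is only one possible handling.

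These objections remove any claim of a demonstrated loss. They do not supply a counting rule, a model type or a rule for leavers' events, and they do not give the baseline term or change score a clear meaning.

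**Conclusion.** The point holds in this form: as specified, the harm comparison uses a baseline term and a change score that have no clear meaning for events accruing after allocation. The SAP contradicts itself on the change score. No stated rule brings events recorded before week 12, or leavers' recorded events, into the comparison of arms.

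How much is lost depends on the reading. It is nothing for completers if the count is cumulative to week 12. At a constant rate it is roughly 70% of events under a four-week look-back and over 90% under a last-week count (100 − 29.6 and 100 − 7.4). These shares rest on assumed rates, the 20% attrition allowance and no use of leavers' records; they are not estimates for this trial. The stronger inference, that early events and leavers certainly fall out of the analysis, is not established.

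Should-fix, with moderate confidence. The outcome is secondary and unpowered and the window is open to interpretation, but the specification needs correcting on either reading.

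**What to change.** In the SAP:

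1. Delete the change score and the baseline term for adverse events.
2. Define the outcome as the number and percentage of all randomised participants, by arm, with at least one recorded adverse event from allocation to week 12 or exit. Use all records: the ongoing record and weeks 4, 8 and 12.
3. Keep leavers' observed events and do not replace them with imputed values. Count a withdrawal due to an event as an event where the reason is recorded; the documents do not show that reasons are collected.
4. Compare each advice arm with control by logistic regression, or by an exact test if events are sparse.
5. Show time at risk beside the counts.
6. Reconcile the SAP's Outcomes section with Analyses One, and the protocol's 6.4 text with Table 2.

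The cost is SAP wording and one tabulation, from data Table 2 already plans to collect. The downside is that leavers have shorter follow-up, so an arm with more early exits can show fewer events for that reason alone. Item 5 makes this visible.
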